As there has been only one documented case of sexual transmission from a woman to a man, and data from the Paz-Bailey paper indicated that ZIKV was recovered only infrequently from cervico-vaginal secretions. Infectious ZIKV was recovered very infrequently from saliva, CVS, and urine following inoculation with ZIKV-SJRP or ZIKV-Nicaragua (Table 5 and Table 7). Shedding of ZIKV in semen will be evaluated in cohorts 3 & 4, which will enroll men. Transmission of both ZIKV strains to mosquitoes will be evaluated in a subset of volunteers in cohorts 3 and 4 to assess the possibility of conducting future ZIKV CHIM studies in the outpatient setting. The peak infectious titers of ZIKV-SJRP recovered from volunteers in cohort 1 were well below $3 \log_{10}$ PFU/mL. Given that mosquitoes ingest only $\sim 2 \mu\text{L}$ per blood meal, it is unlikely that virus at this low titer will be transmitted to mosquitoes. Peak titers of infectious ZIKV-Nicaragua were significantly higher than those of ZIKV-SJRP and it is likely that this virus will be transmitted to mosquitoes from volunteers enrolled in cohort 4. Volunteers in cohorts 3 and 4 will be housed in an inpatient unit from inoculation day through Study Day 8 to reduce the risk of mosquito transmission, as was recommended by the ethics consultation. Volunteers will not be discharged from the unit until ZIKV titer in serum, urine, saliva, semen, and cervico-vaginal secretions is $< 1.4 \times 10^6$ genomic copies/mL. Additional components of the risk mitigation strategy can be found in Section 10.3.7.

In characterizing the 2 ZIKV strains that will be studied in this protocol, we will conduct sampling of blood, urine, cervico-vaginal secretions, semen, and saliva at multiple time-points throughout the 6-month duration of subject participation to determine the quantity and duration of shedding of ZIKV in these samples. Detection of ZIKV in these samples will be performed by RT-PCR as well as by culture of the virus to determine the shedding of infectious virus. The incidence of symptomatic illness will be determined, and the clinical characteristics of illness

will be described. The data obtained from this study will inform the scientific community regarding the sites, magnitude, and duration of infectious ZIKV in women and men. Should a safe and effective ZIKV CHIM be developed, it would be extremely valuable in the down-selection of candidate vaccines and therapeutics and could be used as a critical component of the pathway to licensure.

1.2 Background: ZIKV Strains

1.2.1 ZIKV-SJRP/2016

ZIKV-SJRP/2016 was isolated from the serum of a previously healthy non-pregnant adult female in São Jose do Rio Preto, (São Paulo State), Brazil who presented with uncomplicated ZIKV infection (fever, rash, and conjunctivitis). The virus was isolated directly from serum, expanded, and biologically cloned at the Laboratory of Infectious Diseases (LID), National Institute of Allergy and Infectious Diseases (NIAID), NIH and the clinical lot was manufactured at Charles River Laboratories (CRL) Biopharmaceutical Services facility in Malvern, PA. The final drug product, ZIKV-SJRP/2016 (Lot ZIKV#117A) was manufactured in qualified Vero cells at CRL using a method developed by LID/NIAID/NIH and CRL.

1.2.1.1 Final Container of ZIKV-SJRP/2016

The Final Drug Product was dispensed as 1.0 mL aliquots of live, Vero Grown Zika virus into 1.8 mL sterile cryovials and stored at $-75^{\circ}\text{C} \pm 15^{\circ}\text{C}$. The titer of ZIKV-SJRP/2016 Lot ZIKV#117A Final Drug Product determined on December 5, 2016 was approximately $10^{5.7}$ PFU/mL.

1.2.1.2 Composition of ZIKV-SJRP/2016

The Final Drug Product composition is a concentration of live, Vero Grown Zika virus, Lot ZIKV#117A in L-15 medium containing 1X SPG (sucrose 0.128M; KH_2PO_4 , 0.0038M; K_2HPO_4 , 0.0072M; mono-sodium glutamate, 0.0054M). The potency of ZIKV-SJRP/2016 (Lot ZIKV#117A) is $10^{5.7}$ PFU/mL.

1.2.1.3 Investigational Product Label of ZIKV-SJRP/2016

[figure not shown]

Figure 3: Label for Final Vial of ZIKV-SJRP/2016 (Enlarged Sample)

1.2.2 ZIKV-Nicaragua/2016

ZIKV-Nicaragua/2016 was isolated from the serum of a previously healthy 9-year-old female patient from Nicaragua who presented with uncomplicated ZIKV infection (fever

only). The virus was isolated from serum, expanded, and biologically cloned at the LID, NIAID, NIH and the clinical lot was manufactured at CRL Biopharmaceutical Services facility in Malvern, PA. The final drug product, ZIKV-Nicaragua/2016 (Lot ZIKV#116A) was manufactured in qualified Vero cells at CRL using a method developed by LID/NIAID/NIH and CRL.

1.2.2.1 Final Container of ZIKV-Nicaragua/2016

The Final Drug Product was dispensed as 1.0 mL aliquots of live, Vero Grown Zika virus into 1.8 mL sterile cryovials and stored at $-75^{\circ}\text{C} \pm 15^{\circ}\text{C}$. The titer of ZIKV-Nicaragua/2016 Lot ZIKV#116A Final Drug Product determined on December 5, 2016 was approximately $10^{6.6}$ PFU/mL.

1.2.2.2 Composition ZIKV-Nicaragua/2016

The Final Drug Product composition is a concentration of live, Vero Grown Zika virus, Lot ZIKV#116A in L-15 medium containing 1X SPG (sucrose 0.128M; KH_2PO_4 , 0.0038M; K_2HPO_4 , 0.0072M; mono-sodium glutamate, 0.0054M). The potency of ZIKV-Nicaragua/2016 (Lot ZIKV#116A) is $10^{6.6}$ PFU/mL.

1.2.2.3 Investigational Product Label of ZIKV-Nicaragua/2016

[figure not shown]

Figure 4: Label for Final Vial of ZIKV-Nicaragua/2016 (Enlarged Sample)

1.3 Rationale

1.3.1 Animal Experience

1.3.1.1 Non-human Primate Study

Four rhesus macaques were infected with 2×10^4 PFU of the Current Good Manufacturing Practice (cGMP) material of either ZIKV-SJRP/2016 or ZIKV-Nicaragua/2016 by subcutaneous injection. The macaques were examined daily and bled daily from Day 2 post-infection through Day 8 post-infection for detection of virus. All 4 animals from each group had ZIKV detectable by viral culture on multiple days from Day 2 through Day 5 post-infection. Peak virus was recovered on Day 3 or Day 4 post-infection (Table 2). It has been our experience from our dengue models that NHP develop viremia earlier than do humans. Of note, the ZIKV that will be administered in this protocol will be first given at a dose 200-fold lower than that which was administered to rhesus monkeys.

Table 2: ZIKV Viremia in Rhesus macaques

ZIKV strain	Dose	Mean Peak Titer (\log_{10} PFU/mL)	Peak Titer (\log_{10} PFU/mL)	Mean Day of Onset	Mean Duration of
-------------	------	---------------------------------------	----------------------------------	-------------------	------------------

					viremia, days (range)
SJRP/2016	20,000 PFU	1.8 ± 0.1	1.9	2.3	3.5 (3 – 4)
Nicaragua/2016	20,000 PFU	2.3 ± 0.1 ¹	2.5	2.0 (all)	3.3 (3 – 4)

PFU = plaque-forming units, ZIKV = Zika virus

¹The mean peak titer of ZIKV SJRP/2016 was significantly lower than that of ZIKV Nicaragua/2016, p < 0.05.

1.3.2 Previous Human Experience

1.3.2.1 DENV-2 Controlled Human Infection Model (CHIM)

We have utilized a DENV-2 and a DENV-3 CHIM to evaluate the protective efficacy of the live attenuated tetravalent dengue vaccine candidates TV003 and TV005. The DENV-2 CHIM virus was derived from DENV-2 Tonga/74, which caused only mild disease during an outbreak in Tonga [46]. Although originally developed as a DENV-2 candidate vaccine, the recombinant virus (rDEN2Δ30) was not attenuated when compared to its wild-type (Wt) parent in rhesus macaques and was not considered for evaluation as a vaccine candidate. However, it was repurposed for use as a DENV-2 challenge virus in the dengue CHIM. rDEN2Δ30 has been administered to more than 50 subjects in 3 different challenge studies. A dose of 1,000 PFU induced viremia in 100% of subjects at a mean peak titer of 2.3 log₁₀ PFU/mL, approximately 100-fold higher than that observed with the attenuated DENV included in TV003 and TV005 [47, 48]. The mean day of onset of viremia was nearly day 5 post-infection and the mean day of peak viremia was nearly 7 days post-infection (Table 3). The level of viremia observed in humans was similar to that observed in rhesus macaques (2.3 log₁₀/mL PFU vs 1.7 log₁₀ PFU/mL) but the duration of viremia was longer in humans (5.2 days vs 2.8 days) [49]. It also induced a mild to moderate rash in 88% of subjects to whom it was administered. Fever was not observed in any subject. Both TV003 and TV005 were demonstrated to protect 100% of vaccinated volunteers against challenge with DEN2Δ30 administered 6 months after vaccination [48].

1.3.2.2 DENV-3 CHIM

The DENV-3 CHIM virus rDEN3Δ30 was derived from a Wt DENV-3 (Sleman/78) that was noted to cause mild illness during its outbreak in Indonesia [50]. It was originally developed as a candidate DENV-3 vaccine virus but was not attenuated in rhesus macaques compared with its Wt parent. It was first evaluated in 10 healthy, flavivirus-naïve subjects at a dose of 1,000 PFU and induced detectable infectious virus in all 10 subjects. The mean peak titer was 0.5 log₁₀ lower than that observed with the DEN2Δ30 and the absolute peak titer was more than a log lower (Table 3). The level of viremia observed in humans was similar to that observed in rhesus macaques (1.77 log₁₀/mL PFU vs 1.5 log₁₀ PFU/mL) but the duration of viremia was slightly longer in humans (3.4 days vs 2.0 days) [51]. A mild to moderate rash was observed in 80% of DEN3Δ30 recipients; fever was not observed in any recipient. The DENV-3 CHIM was utilized at a dose of 10,000 PFU to evaluate the protective efficacy of TV005 against DENV-3. TV005 elicited 100% protection against challenge with DENV-3 at 6 months.

Table 3: Viremia Induced by the DENV-2 and DENV-3 CHIM Viruses in Normal Healthy Volunteers

Virus	N	Dose	Mean peak titer \pm SE (\log_{10} PFU/mL)	Peak titer (\log_{10} PFU/mL)	Mean day of peak titer \pm SE	Mean Day of onset \pm SE	Mean duration of viremia, days \pm SE
rDEN2Δ30	57	1,000 PFU	2.31 \pm 0.07	3.3	6.9 \pm 0.2	4.9 \pm 0.3	5.2 \pm 0.3
rDEN3Δ30	10	1,000 PFU	1.77 \pm 0.15	2.1	5.3 \pm 0.3	4.6 \pm 0.4	3.4 \pm 0.6

N = number of subjects, PFU = plaque-forming units, SE = standard error

1.3.2.3 ZIKV-SJRP (Cohort 1)

ZIKV-SJRP or placebo was administered to 14 women in cohort 1 randomized 5:2 in 2 blocks of volunteers. Ten women received ZIKV-SJRP and 4 women received placebo. Adverse events following administration of ZIKV-SJRP or placebo are shown in Table 4. ZIKV-like rash was observed in 9/10 volunteers who received ZIKV-SJRP and was the most common adverse event related to ZIKV-administration. Non-purulent conjunctivitis occurred in 50% of ZIKV-SJRP recipients, arthralgia in 70% and myalgia in 50%. Fever was not observed nor were any signs or symptoms consistent with GBS.

ZIKV-SJRP was recovered from 100% of those who received the virus. Both infectious virus and virus detected by PCR were recovered from the serum of all 10 infected volunteers (Figure 5). The virus detected by PCR was below the cut-off for discharge from the inpatient unit at all times post-administration. Infectious virus titer peaked at day 5 in 6/10 volunteers. The mean peak titer was 46.8 PFU/mL (1.67 \log_{10} PFU/mL). Peak virus titer was below 100 PFU/mL (2 \log_{10} PFU/mL) in 8/10 volunteers and below 1,000 PFU/mL (3 \log_{10} PFU/mL) in the remaining 2 volunteers. Infectious ZIKV-SJRP was found infrequently in CVS, saliva, and urine (Table 5). ZIKV-SJRP was found by qPCR in urine, saliva, and CVS in 80%, 70%, and 50% of women, although the titers were low and the duration of shedding short (Table 5). ZIKV-SJRP was not recovered from any specimen taken from placebo recipients. The low peak titer following inoculation with 100 PFU of ZIKV-SJRP suggests that challenge studies may be safely performed in an outpatient setting.

Table 4: All Adverse Events Following One Dose of Cohort 1 (ZIKV-SJRP/placebo) (CIR 316)

	ZIKV-SJRP (n=10) N (%)	Placebo (n=4) N (%)	P value (1-sided) ¹
Local			
Erythema	1 (10.0%)	0 (0.0%)	0.7143
Tenderness	1 (10.0%)	0 (0.0%)	0.7143
Pain	0 (0.0%)	0 (0.0%)	n/a
Pruritus	0 (0.0%)	0 (0.0%)	n/a
Induration	0 (0.0%)	0 (0.0%)	n/a
Systemic			
Fever	0 (0.0%)	0 (0.0%)	n/a
Headache	9 (90.0%)	3 (75.0%)	0.9341
Zika-like Rash	9 (90.0%)	0 (0.0%)	0.0050
Neutropenia ²	1 (10.0%)	0 (0.0%)	0.7143

	ZIKV-SJRP (n=10) N (%)	Placebo (n=4) N (%)	P value (1-sided) ¹
Nonpurulent conjunctivitis	5 (50.0%)	0 (0.0%)	0.1259
Elevated ALT	0 (0.0%)	1 (25.0%)	1.0000
Myalgia	5 (50.0%)	0 (0.0%)	0.1259
Arthralgia	7 (70.0%)	0 (0.0%)	0.0350
Retro-orbital Pain	4 (40.0%)	0 (0.0%)	0.7203
Fatigue	5 (50.0%)	2 (50.0%)	0.4286
Muscle weakness	1 ³ (10.0%)	0 (0.0%)	0.7143
Prolonged PT	0 (0.0%)	0 (0.0%)	n/a
Hyporeflexia	0 (0.0%)	0 (0.0%)	n/a
Prolonged PTT	0 (0.0%)	0 (0.0%)	n/a
Thrombocytopenia	0 (0.0%)	0 (0.0%)	n/a

1. Greater for ZIKV-SJRP

2. Neutropenia was defined as an ANC $\leq 1,000/\text{mm}^3$.

3. Muscle weakness was reported by the volunteer but was not detected on physical examination. It lasted 1 day.

[figure not shown]

Figure 5: Kinetics of ZIKV-SJRP in Serum by Culture and Quantitative PCR

Table 5: Recovery of ZIKV-SJRP from Serum, Whole Blood, CVS, Saliva, and Urine
ZIKV-SJRP recovered by virus culture (infectious virus) (Day 0 – 28)

Sample	Frequency (N=10)	Mean peak titer (\log_{10} PFU/mL)	Mean day of onset	Mean duration (days)	Duration range (days)
Serum	100%	1.67	4.0	4.7	4 - 6
Whole blood	40%	1.7	5.3	2.3	1 - 3
CVS	10%	2.30	10.0	1.0	1 - 1
Saliva	30%	0.50	8.7	1.0	1 - 1
Urine	10%	0.7	10.0	3.0	3 - 3
ZIKV-SJRP recovered by quantitative PCR (Day 0 – 28)					
Serum	100%	5.11	2.5	7.5	7 - 10
Whole blood	100%	4.19	4.2	7.8	4 - 15
CVS	50%	2.72	10.7	3.8	1 - 7
Saliva	70%	2.69	10.3	1.9	1 - 5
Urine	80%	3.00	11.5	3.4	1 - 10

1.3.2.4 ZIKV-Nicaragua (Cohort 2)

ZIKV-Nicaragua or placebo has been administered to 14 women in cohort 2 randomized 5:2 in 2 blocks of volunteers. Ten women received ZIKV-Nicaragua and 4 women received placebo, however the treatment assignment has been unblinded for only 7 of the 14 volunteers at this time. Adverse events following administration of ZIKV-Nicaragua or placebo are shown in [Table 6](#). ZIKV-like rash was observed in 5/5 volunteers who received ZIKV-Nicaragua and was the most common adverse event related to ZIKV-administration. Myalgia in 80% of ZIKV-Nicaragua recipients and arthralgia was observed in 60%. Fever was not observed nor were any signs or symptoms consistent with GBS. Non-purulent conjunctivitis was not observed in recipients of ZIKV-Nicaragua.

ZIKV-Nicaragua was recovered from the serum and whole blood of 5/5 volunteers who received the virus (100%). Both infectious virus and virus detected by quantitative PCR were recovered from the serum of all 5 infected volunteers (Figure 6). The virus detected by PCR was above the cut-off for discharge from the inpatient unit ($> 6.4 \log_{10}$ GEQ/mL) for only 1 time-point for only 2 volunteers (both day 6). The titer was below the cut-off for discharge for all other time-points and all other volunteers. The mean peak titer of infectious ZIKV-Nicaragua in the serum was 4,266 PFU/mL ($3.63 \log_{10}$ PFU/mL) which was significantly higher than that of ZIKV-SJRP (46.8 PFU/mL; $1.67 \log_{10}$ PFU/mL), $\alpha = 0.01$. The higher infectious peak titer following inoculation with 100 PFU of ZIKV-Nicaragua suggests that this virus is likely to be transmitted to mosquitoes. The mean peak titer in serum by quantitative PCR was also significantly higher for ZIKV-Nicaragua compared with ZIKV-SJRP ($6.29 \log_{10}$ GEQ/mL vs $5.11 \log_{10}$ GEQ/mL, respectively, $\alpha=0.01$).

Table 6: All Adverse Events Following One Dose of Cohort 2a (ZIKV-Nicaragua/Placebo) (CIR 316)

	ZIKV-Nicaragua (n=5) N (%)	Placebo (n=2) N (%)	P value (1-sided) ¹
Local			
Erythema	0 (0.0%)	0 (0.0%)	n/a
Tenderness	0 (0.0%)	0 (0.0%)	n/a
Pain	0 (0.0%)	0 (0.0%)	n/a
Pruritus	0 (0.0%)	0 (0.0%)	n/a
Induration	0 (0.0%)	0 (0.0%)	n/a
Systemic			
Fever	0 (0.0%)	0 (0.0%)	n/a
Headache	4 (80.0%)	2 (100.0%)	1.0000
Zika-like Rash	5 (100.0%)	0 (0.0%)	0.0476
Neutropenia ²	0 (0.0%)	0 (0.0%)	n/a
Nonpurulent conjunctivitis	0 (0.0%)	1 (50.0%)	1.0000
Elevated ALT	2 (40.0%)	0 (0.0%)	0.4762
Myalgia	5 (100.0%)	1 (50.0%)	0.2857
Arthralgia	3 (60.0%)	0 (0.0%)	0.2857
Retro-orbital Pain	4 (80.0%)	1 (50.0%)	0.9524
Fatigue	5 (100.0%)	2 (100.0%)	n/a
Muscle weakness	0 (0.0%)	0 (0.0%)	n/a
Prolonged PT	0 (0.0%)	0 (0.0%)	n/a
Hyporeflexia	0 (0.0%)	0 (0.0%)	n/a
Prolonged PTT	0 (0.0%)	0 (0.0%)	n/a
Thrombocytopenia	0 (0.0%)	0 (0.0%)	n/a

1. Greater for ZIKV-Nicaragua

2. Neutropenia was defined as an ANC \leq 1,000/mm³.

[figure not shown]

Figure 6: Kinetics of ZIKV-Nicaragua in Serum by Culture and Quantitative PCR

Table 7: Recovery of ZIKV-Nicaragua from Serum, Whole Blood, CVS, Saliva, and Urine

ZIKV-Nicaragua recovered by virus culture (infectious virus) (Day 0 – 28)					
Sample	Frequency (N=5)	Mean peak titer (log ₁₀ PFU/mL)	Mean day of onset	Mean duration (days)	Duration range (days)
Serum	100%	3.63	4.04	3.0	5.4
Whole blood	100%	3.52	3.90	4.4	4.2
CVS	0%	n/a	n/a	n/a	n/a
Saliva	100%	0.58	0.70	8.0	3.4
Urine	20%	0.50	0.50	6.0	1.0
ZIKV-Nicaragua recovered by quantitative PCR (Day 0 – 28)					
Serum	100%	6.29	6.57	2.4	11.4
Whole blood	100%	5.62	6.21	3.2	8.8
CVS	80%	2.43	2.89	8.5	4.0
Saliva	100%	2.71	3.80	10.8	2.2
Urine	80%	2.86	4.23	8.0	5.5

2 OBJECTIVES

2.1 Primary Objectives

- Determine the suitability of both ZIKV strains for use in a safety-assured Zika CHIM. Suitability will be assessed by:
 - The frequency and severity of clinical signs and symptoms of infection such as fever, rash, conjunctivitis, myalgia, arthralgia, and headache following ZIKV administration compared with placebo.
 - The infection frequency of ZIKV by strain and by dose. Infection is defined as recovery of ZIKV (determined by RT-PCR or culture) from blood, urine, cervico-vaginal secretions, semen, or saliva and/or by seroconversion to ZIKV (50% plaque reduction neutralization titer [PRNT₅₀] ≥ 1:10) by 90 days post-administration of the ZIKV strain.

- The frequency, magnitude, and duration of ZIKV presence in the blood, urine, cervico-vaginal secretions, semen, and saliva by both RT-PCR and virus titration in tissue culture by ZIKV strain and dose.
- A suitable ZIKV CHIM strain is defined as one that:
 - a. $\geq 80\%$ of ZIKV and DENV-naïve inoculated subjects develop detectable viremia by virus culture (infectious virus) **and**
 - b. Infectious virus is detected on more than 1 day for $\geq 80\%$ of subjects with detectable viremia **and**
 - c. The mean peak titer of infectious virus recovered from subjects is $2 - 3.0 \log_{10}$ PFU/mL

Ideally $\geq 50\%$ of ZIKV and DENV-naïve inoculated subjects will develop ≥ 1 of the following clinical signs thought to be definitely, probably, or possibly due to the ZIKV strain, however this will not be required for dose expansion or dose escalation:

 - i. Fever
 - ii. Rash
 - iii. Non-purulent conjunctivitis
 - iv. Myalgia
 - v. Arthralgia

A mean peak titer of $2.0 - 3.0 \log_{10}$ PFU/mL should ensure that virus is readily detected but at a level that reduces the risk of symptomatic illness and virus transmissibility.

2.2 Secondary Objectives

- Characterize the clinical presentation of acute ZIKV infection by assessing the frequency of adverse events (AEs), graded by severity, occurring within 28 days of ZIKV administration.
- Determine the quantity and duration of ZIKV presence as determined by:
 - The peak virus titer in the blood and the duration of viremia induced by the ZIKV strain at each tested dose as determined by RT-PCR and virus culture
 - The quantity and duration of ZIKV shedding in saliva determined by RT-PCR and virus culture
 - The quantity and duration of ZIKV shedding in urine determined by RT-PCR and virus culture
 - The quantity and duration of ZIKV shedding in cervico-vaginal secretions determined by RT-PCR and virus culture
 - The quantity and duration of ZIKV shedding in semen determined by RT-PCR and virus culture
- Evaluate the kinetics of the serum neutralizing antibody response following primary ZIKV infection and determine the peak neutralizing antibody response to ZIKV through Study Day 90.

2.3 Exploratory Objectives

The exploratory objectives of this study are the following:

- Evaluate the cellular immune response to primary infection with ZIKV.
- Evaluate the innate immune response to primary infection with ZIKV.

- Evaluate B and T cell memory responses following primary infection with ZIKV.
- Evaluate the antibody repertoire induced by ZIKV infection.
- Evaluate the antibody response in saliva to primary infection with ZIKV as a possible diagnostic tool. This will be done in a subset of subjects (those enrolled at the Center for Immunization Research [CIR]).
- Evaluate the transmissibility of ZIKV-SJRP and ZIKV-Nicaragua from infected volunteers to mosquitoes.

3 STUDY DESIGN

3.1 Receipt of Test Article

3.1.1 Overall Design

This study is a placebo-controlled, double-blind study in normal healthy adult male and non-pregnant female subjects 18 - 40 years of age, inclusive, recruited from the metropolitan Baltimore/Washington, DC and Burlington, VT areas. The purpose of this study is to evaluate the clinical and virologic response to escalating doses of 2 different ZIKV strains administered subcutaneously in healthy, ZIKV and DENV-naïve, male and non-pregnant, female adult volunteers to identify the most suitable ZIKV strain and dose for use in a ZIKV CHIM. The ZIKV CHIM will then be used to evaluate the protective efficacy of candidate ZIKV vaccines prior to evaluation of these candidates in Phase 2 clinical trials. Placebo recipients are included in the study as a control to better assess ZIKV-associated versus non-ZIKV-associated AEs. After providing written informed consent, subjects will undergo eligibility screening, including medical history, physical examination, hematology testing, liver and renal function testing, human immunodeficiency virus (HIV) screening, hepatitis B and C screening, urinalysis, urine toxicology screening for opiates and serology screening for previous ZIKV or DENV infection. Serum pregnancy testing will be performed on applicable female subjects. All screening tests must be performed within 60 days of inoculation. HIV screening must be performed within 2 weeks of inoculation. Pregnancy screening will be repeated within 14 days prior to inoculation and on the day of inoculation.

All clinically significant abnormalities will be reviewed with subjects and referral for follow-up care will be provided. Subjects will be determined to be eligible based on the inclusion and exclusion criteria found in Section 4 of this protocol. For subjects who are eligible, the Day 0 visit will be scheduled for receipt of inoculation. Serum pregnancy testing will be repeated on female subjects on the day of inoculation and during follow-up. Subjects will be considered enrolled in the study only after they receive test article (ZIKV or placebo). Subjects will present to the unit on Study Day 0. After eligibility criteria have been reviewed and confirmed, they will be inoculated with test article on Study Day 0. Until mosquito-transmissibility data are available, subjects will be admitted to the inpatient unit and will be kept in the inpatient unit through Study Day 9 (discharged on Study Day 9, for a total of 9 nights), the period of time when viremia is expected to be present and at a level that would be transmissible to mosquitoes. If mosquito-transmissibility data from cohorts 3 and 4 demonstrate that ZIKV-SJRP or ZIKV-Nicaragua cannot escape the mid-gut barrier of the mosquito, additional studies of these ZIKV may be considered for outpatient evaluation for the duration the subjects' enrollment. The protocol will be revised to include an outpatient enrollment if the transmissibility studies support this.

For the inpatient portion of the study, subjects will remain in the inpatient unit from Study Day 0 through Study Day 9 (9 nights, discharged on Study Day 9). If they meet discharge criteria (See

Section 6.4.2), they will be discharged from the inpatient unit on Study Day 9. They will be evaluated every day during the inpatient stay and will be seen again on Study Day 9, Study Day 10, Study Day 12, Study Day 14, and Study Day 16. During the outpatient and inpatient visits through Study Day 28, the subjects will be evaluated by a clinician and will have blood drawn for clinical laboratory studies, virologic assays, and immunologic assays. In addition, urine, cervico-vaginal secretions, semen, and saliva will be collected at specific time points for additional virologic assays (see Section 6 for a detailed description of study procedures). Subjects will return to the clinic on Study Days 21, 28, 35, 56, 70, 90, 120, and 180 for evaluation, blood and specimen collection. Study Day 180 will be their final visit. Subjects will have their temperature measured and recorded at least twice a day during their inpatient stay, with the exception of day of discharge. Temperature will be recorded once by study staff prior to discharge.

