3.1.2.1 Initial Enrollment of Each Cohort

For each cohort, only the first 7 subjects (5 ZIKV recipients; 2 placebo recipients) will be enrolled until all 7 subjects have completed Study Day 28 and the criteria listed in Section 3.1.2.2 have been met. If the criteria to enroll the remaining 7 subjects from a dose cohort are met, enrollment will proceed. For cohorts 3 and 4, mosquito-feeding will be performed on a subset of enrolled volunteers. A total of 7 volunteers (randomized 5:2 ZIKV:placebo) from cohort 3 and 7 volunteers (randomized 5:2 ZIKV:placebo) from cohort 4 will undergo mosquito-feeding.

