6.7 Mosquito Feeding

Feeding of mosquitoes on a subset of subjects enrolled in cohorts 3 and 4 will be conducted as described for rDEN4 Δ 30 except the days of feeding will be different [52]. Seven subjects from cohort 3 and seven subjects from cohort 4 (each randomized 5:2 ZIKV:placebo) will be selected for mosquito feeding. Inclusion of placebo recipients in the mosquito-feeding will be done to ensure the clinical team remains blinded to treatment assignment. Five to 7 day-old female *Aedes albopictus* mosquitoes will be brought to the inpatient unit from the insectory of the Laboratory of Viral Diseases, National Institutes of Health on study days 5, 6, and 7. Each subject will have a pint container holding ten to fifteen *Aedes albopictus* mosquitoes placed on the ventral surface of their forearm. The mosquitoes will be allowed to feed for 10 minutes. This will be performed on study days 5, 6, and 7. After feeding, the container will be placed at -20°C for a few minutes to “anesthetize” the mosquitoes. After removing the container from the -20° freezer, unfed and partially engorged mosquitoes will be removed from the containers and destroyed. Fully engorged mosquitoes will remain in the containers and will be immediately returned to the LVD

where they will be housed and maintained in the LVD insectory per LVD standard protocol. Twenty-one days later the head and midgut tissues of the mosquitoes will be examined for the presence of ZIKV antigens. Methods for detection of ZIKV may include polymerase chain reaction, immunofluorescence staining, and culture.

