The study is powered to detect a difference in the occurrence of virus in blood, urine, cervico-vaginal secretions, or saliva following administration of one of 2 ZIKV at different doses, compared with placebo recipients. A sample size of 10 ZIKV recipients and 4 placebo recipients will be able to detect a statistically significant difference ($\alpha = 0.05$) in recovery of infectious ZIKV from the blood between the ZIKV and placebo groups at a power of 0.99 with $\geq 80\%$ of ZIKV-inoculated subjects having detectable ZIKV viremia and 0 placebo recipients having detectable ZIKV in blood and body secretions. The detection of ZIKV by RT-PCR and by virus culture from blood, urine, cervico-vaginal fluids, semen and saliva in recipients of each ZIKV strain will be compared to placebo recipients. In addition, the magnitude and duration of ZIKV presence in blood, urine, cervico-vaginal secretions, semen and saliva will be compared to one another at each dosing level. The effect of dose escalation on the presence of virus in blood, urine, saliva, cervico-vaginal secretions and semen will also be evaluated. Multiple comparisons analysis will be used to compare the magnitude and duration of virus presence at each dose level of each candidate ZIKV and placebo recipients.

Measuring the transmissibility of ZIKV-SJRP and ZIKV-Nicaragua from infected volunteers to mosquitoes is an exploratory endpoint. Following feeding on volunteers, mosquitoes will be returned to the NIH for analysis (Section 6.7). The heads and thoraces of the mosquitoes will be examined for ZIKV antigen. If antigen is detected in the head of the mosquitoes, it will be assumed that the virus escaped the mid-gut barrier and is present in the salivary glands.

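### The two mosquito sections list different tissues, and five ZIKV recipients per strain cannot show that a strain is unable to escape the midgut

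*Combined protocol and SAP*

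**What the plan says.** Section 3.1.1 keeps volunteers in the inpatient unit until mosquito data exist. It then says what follows if the feeding results in the two male groups "demonstrate that ZIKV-SJRP or ZIKV-Nicaragua cannot escape the mid-gut barrier of the mosquito, additional studies of these ZIKV may be considered for outpatient evaluation". The sentence after that requires the protocol to be revised before any outpatient enrollment.

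Two sections describe the laboratory examination:

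- Section 6.7: "Twenty-one days later the head and midgut tissues of the mosquitoes will be examined for the presence of ZIKV antigens".
- Section 9.2: "The heads and thoraces of the mosquitoes will be examined for ZIKV antigen".

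Section 9.2 also supplies the reading rule: "If antigen is detected in the head of the mosquitoes, it will be assumed that the virus escaped the mid-gut barrier". It labels transmissibility an exploratory endpoint.

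Neither section gives a denominator, a minimum number of analysable mosquitoes, a unit of analysis or a confidence bound. Section 6.7 refers to the method of a cited dengue-4 vaccine-candidate study, with different feeding days. That source cannot be checked here.

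**The concern.** The condition in Section 3.1.1 is about a barrier. To say that virus did not cross the midgut, one must know that it was in the midgut. The tissue list in Section 9.2 does not provide this, and the list in Section 6.7 does. A laboratory or analyst who followed Section 9.2 alone would hold head results without the denominator that the claim needs.

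The wording also asks for proof of absence. A null result from five infected men is compatible with a substantial share of men being able to infect mosquitoes, and the plan states no bound that would tell a reader how large.

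The result has a use beyond description. Section 1.1 says feeding is done to assess whether later challenge studies could be outpatient, and Section 10.3.6.4 ties inpatient housing to these data. Third-party transmission by mosquito is among the main risks that Section 1.1 reports from the ethics consultation.

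**Working it through.** The documents give no sample size, power, margin or bound for mosquito feeding, so there is no stated figure to reproduce.

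**Inputs**

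- Volunteers (Section 3.1.2.1): "A total of 7 volunteers (randomized 5:2 ZIKV:placebo) from cohort 3 and 7 volunteers (randomized 5:2 ZIKV:placebo) from cohort 4 will undergo mosquito-feeding". That is 5 ZIKV recipients per strain. The 2 placebo recipients are there to protect the blind.
- Mosquitoes (Section 6.7): "Each subject will have a pint container holding ten to fifteen" mosquitoes, and "This will be performed on study days 5, 6, and 7". The ceiling per strain is 5 × 3 × 10 = 150 to 5 × 3 × 15 = 225.
- Losses (Section 6.7): "unfed and partially engorged mosquitoes will be removed from the containers and destroyed". No engorgement or survival rate is given.
- ZIKV-SJRP titre in cohort 1 (Section 1.3.2.3): mean peak 46.8 PFU/mL; 8 of 10 recipients peaked below 100 PFU/mL and the other 2 below 1,000.
- Blood meal (Section 1.1): about 2 µL, or 0.002 mL.

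**Step 1: what each tissue list can distinguish**

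| True state of mosquito | Head | Midgut | Separable under 6.7 | Separable under 9.2 |
|---|---|---|---|---|
| Never infected | negative | negative | yes | no |
| Infected, not disseminated | negative | positive | yes | no |
| Disseminated | positive | positive | yes | yes |

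Neither section says how a mosquito with a positive thorax and a negative head would be classed.

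**Step 2: why the first two rows matter for ZIKV-SJRP**

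Expected infectious virus per meal is titre × 0.002 mL. Assuming a Poisson count, the chance that a meal carries at least one PFU is 1 − exp(−mean).

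- At 46.8 PFU/mL: 46.8 × 0.002 = 0.094 PFU; 1 − exp(−0.094) = about 9%.
- At 100 PFU/mL: 0.2 PFU; about 18%.
- At 1,000 PFU/mL: 2 PFU; about 86%.

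At the mean peak, roughly nine meals in ten would contain no infectious virus. A head-negative mosquito from such a meal says nothing about the barrier.

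**Step 3: zero of five volunteers**

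The exact (Clopper-Pearson) upper limit with no events is 1 − α^(1/n).

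- One-sided 95%: 1 − 0.05^(1/5) = 0.451.
- Upper end of the two-sided 95% interval: 1 − 0.025^(1/5) = 0.522.

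The chance of seeing none in five when a share p of men could transmit is (1 − p)^5. The values of p are assumptions.

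- p = 20%: 0.8^5 = 0.328.
- p = 30%: 0.7^5 = 0.168.
- p = 40%: 0.6^5 = 0.078.

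**Step 4: does counting mosquitoes rescue the wording?**

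Mosquitoes fed on one man share his viremia. With M analysable mosquitoes per man and within-volunteer correlation ICC, the effective number is 5M / (1 + (M − 1) × ICC). The one-sided 95% limits below assume that every mosquito is engorged and survives (M = 30 to 45).

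| Assumed ICC | Upper limit per mosquito |
|---|---|
| 0 | 1.3% to 2.0% |
| 0.1 | about 7% |
| 0.2 | 12% to 13% |
| 0.5 | 26% to 27% |
| 1 | 45% |

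If half were analysable, the ICC = 0 limits would be 2.6% to 3.9%. These limits describe the chance per mosquito, a different quantity from the share of men in Step 3. None of them amounts to *cannot*.

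**The case against.** Three stronger readings are tempting, and the documents support none of them.

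*The outpatient condition is unsupported.* A reader might infer this from 0 of 5. But the text is permissive, the endpoint is exploratory, and Section 3.1.1 requires a protocol revision, which under Section 8.5 needs prior sponsor and IRB approval. The protocol also has separate evidence for ZIKV-SJRP. All ten cohort 1 recipients peaked below 1,000 PFU/mL, while Section 10.3.6.4 puts the level needed for transmission at generally above 3 log10 PFU/mL. For ZIKV-Nicaragua the protocol expects transmission, so a null result is mainly a question for one strain.

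*The tissue conflict removes the deciding measurement.* It does not. Head antigen defines escape and both sections examine the head. It can also be argued that, for third-party risk, a never-infected mosquito and a blocked one are equally harmless. That is fair for the mosquitoes actually fed. It does not rescue the statement in Section 3.1.1, which is about the barrier itself. If few mosquitoes were infected, the barrier was scarcely tested.

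*The plan would count mosquitoes as independent and report a limit of 1.3% to 2.0%.* No section proposes this. Setting that range against 45% also mixes two quantities, the chance per mosquito and the share of men, so the ratio does not measure an error.

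A practical objection stands as well. With zero events in five clusters the within-volunteer correlation cannot be estimated, so any mosquito-level bound must rest on an assumed value.

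**Conclusion.** The point holds in a limited form. Sections 6.7 and 9.2 contradict each other on tissues and must be reconciled. Without the midgut, the claim in Section 3.1.1 cannot be evaluated, chiefly for ZIKV-SJRP. Separately, the wording claims more than five recipients per strain can give: a null result leaves up to 45% (one-sided) or 52% (two-sided) of men as possible sources of a disseminated mosquito.

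The 45% and 52% rest only on five independent volunteers, all infected and all with analysable mosquitoes; with fewer, the limits widen. The 33% chance of a null rests on an assumed 20% of men able to transmit. The documents do not state that rate, although 2 of 10 women in cohort 1 had the higher peak titres and the Precis expects similar kinetics in men. The 9% of meals rests on the Poisson assumption and on cohort 1 titres.

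This should be corrected before the cohort 3 and 4 mosquitoes are analysed. It does not invalidate the feeding study.

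**What to change.** 1. Use one tissue list in Sections 6.7 and 9.2: head and midgut, with thorax optional. If the thorax is kept, say how a thorax-positive, head-negative mosquito is classed.
2. Report midgut infection among analysed mosquitoes, and dissemination among those with an infected midgut, as separate results.
3. Make the volunteer the unit for the main summary: the proportion of viremic ZIKV recipients with at least one disseminated mosquito, by strain, with an exact 95% confidence interval.
4. Give mosquito counts by volunteer and same-day titre descriptively. Show any mosquito-level bound over a range of assumed within-volunteer correlation, labelled as assumed.
5. In Section 3.1.1, replace the claim that a strain cannot escape with a statement of the number of the five volunteers in whom dissemination was not detected and the 95% upper limit. Any protocol revision would consider it together with the titre data.

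This needs no extra feeding, only wording and a little more analysis, plus midgut examination if Section 9.2 was the version being followed. The price is a weaker permitted conclusion. Nothing here proposes where future volunteers should be housed.
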